Subject Enrollment																				
Follow up studies																				
Longitudinal follow up																				
Reports for DSMB																				
Statistical Analysis																				
Interpretation of Results																				
Progress Reports																				
Dissemination of results																				

B. Specific Aims

Specific Aim 1: To determine the short and long term effects of ZA on BMD values of the hip, distal femur and proximal tibia in patients with acute SCI relative to patients receiving placebo.

Primary hypothesis: Subjects treated with ZA will have at least a 50% smaller percentage decline in BMD values for the hip, distal femur and proximal tibia at 4 and 12 months post-injury than control subjects.

Secondary hypothesis 1: Subjects treated with ZA will maintain original BMD values for the hip, distal femur and proximal tibia at 4 months and lose no more than 5% at 12 months post-injury than control subjects.

Secondary hypothesis 2 (Exploratory): Incidence of fractures in the hip, distal femur, and proximal tibia will be at least 50% lower in subjects treated with ZA compared to controls. This final hypothesis is exploratory, since we do not expect to have the numbers to achieve statistical significance given the relatively low frequency of sub-lesional fractures in SCI.

Specific Aim 2: To measure and compare selected blood biomarker levels: 1) pro-osteoclastogenic factor IL-1 β ; 2) bone formation marker P1NP; and 3) bone resorption marker serum C terminal telopeptide of type I collagen (s-CTX) in subjects treated with ZA to control subjects.

Primary hypothesis: Subjects treated with ZA will have lower levels of serum marker of bone resorption s-CTX at 4 and 12 months, relative to controls. *In terms of absolute marker levels*, we hypothesize that the ZA subjects will have s-CTX values within the reference range at 4 and 12 months, in contrast to control subjects whose resorption marker levels will be significantly above the reference range at all of the time points.

Secondary hypothesis: Levels of serum marker of bone formation P1NP will not be lower than control subjects at 4 and 12 months.

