- Subjects will be assessed for participation in physical therapy and occupational therapy since receiving the study drug, as well as willingness to get study drug again via interview held 7 days following infusion.

E. Days 1, 3, 7, 14, Post-Drug Infusion

- Subjects will be assessed weekly for one month after study drug administration for known side effects of the drugs, including myalgias, fever, gastrointestinal disturbances, and flu-like symptoms.
- Laboratory values will be drawn for serum calcium, phosphate, and magnesium.

F. Month 1 Post Injury (+/-4 days)

- Subjects will be assessed weekly for one month after study drug administration for known side effects of the drugs, including myalgias, fever, gastrointestinal disturbances, and flu-like symptoms.
- Blood samples* for laboratory values will be drawn for s-CTX, IL-1 β , 25-OH vitamin D, serum calcium, intact parathyroid hormone, and Serum P1NP. *The total amount of blood drawn for all laboratory tests will be < 25 ml at each data collection session.

G. Month 2, 6 & 10 Post Injury

A patient questionnaire will be administered either in-person or by telephone. The questions cover:

- Any evidence or knowledge of bone fractures since the previous contact.
- Information about exercises and standing, including use of functional electrical stimulation (FES), such as how often and average daily duration.
- Supply of vitamin D and calcium tablets with reminder to bring pill bottles with them to clinic for follow up assessments and study sponsored refill of medications. At these follow up visits, pill counts will be done to assess their compliance with medication use.

H. Months 4 & 12 Post Injury

- Blood sample will be drawn for s-CTX, 25-OH vitamin D, serum calcium, intact parathyroid hormone. Serum P1NP will also be drawn at 4 months. The total amount of blood drawn for all laboratory tests will be < 25 ml at each data collection session.
- Complete neurological exam (at 12 months only)
- A patient questionnaire will be administered.
- DXA scan

I. Month 8 Post Injury

- Blood sample will be drawn for 25-OH vitamin D and serum calcium. The total amount of blood drawn for all laboratory tests will be < 25 ml at each data collection session.

J. Serum 25-OH Vitamin D Monitoring and Supplements

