Since serum 25OH vitamin D represents a storage level of vitamin D accumulated over the preceding months, subjects with therapeutic values immediately after injury may have normal vitamin D stores which decline in subsequent months. For this reason, vitamin D levels in all subjects will be monitored not only at baseline but also at months 1, 4, 8 and 12. Subjects will be supplemented with 50,000 IU oral ergocalciferol weekly, if insufficient (serum level 13-20 ng/ml); 2000 IU cholecalciferol or ergocalciferol daily, if sub-therapeutic (serum vitamin D level 21-31ng/ml). Those subjects in the therapeutic range for serum 25-OH vitamin D will be given a maintenance dose of 1000 IU oral vitamin D daily.

Table 4: Study Events and Visit Schedule

	Screening (Day 0-17)	Baseline (Day 8-21)	Study Drug and Acetaminophen Administration (within 21 days of injury)	1 month + / - 4 days	4 months + / - 7 days	8 months + / - 14 days	1 year + / - 14 days
Medical History Standard Care	X						
Physical Exam Standard Care	X						
Basic Metabolic and Hepatic Panel) Standard Care	X						
FRAX Score		X					
Study Drug Infusion			X				
Acetaminophen Administration			X ^a X ^b				
Serum calcium, magnesium, phos Standard Care	X	X		X	X	X	X
Serum 25OH-D Standard Care	X			X	X	X	X
Serum iPTH ^d Study Specific	X			X	X		X
P1NP ^e Study Specific		X		X	X		
IL-1 beta ^f Study Specific		X		X			
Serum CTX ^g Study Specific		X		X	X		X
CPK ^h Study Specific		X					
DXA** Study Specific		X ^c			X		X

- a) Administered every 4 hours for the first 24 hours following study drug infusion
- b) Administered every 4 hours PRN through day 3 following study drug infusion
- c) To be obtained as soon as medically stable to undergo DXA testing
- d) iPTH Blood Test Intact parathyroid hormone
- e) P1NP Blood Test N-terminal propeptide of Type I collagen
- f) IL-1 beta Blood Test Interleukin 1 beta
- g) S-CTX Blood Test Serum carboxy-terminal telopeptide of type I collagen
- h) CPK Blood Test Creatinine Phosphokinase

Table 5 Schedule of follow up contacts for **Years 2 through 4** of the study.

	Year 1 Every 2 Months	Year 2 Month 6	Year 2 Month 12	Year 3 Month 6	Year 3 Month 12	Year 4 Month 6	Year 4 Month 12
Questions about fractures	X	X	X	X	X	X	X
Questions about Vitamin D/calcium supplements	X	X	X	X	X	X	X
Questions about exercise and other treatments	X	X	X	X	X	X	X

Questions about functional status	X	X	X	X	X	X	X
-----------------------------------	---	---	---	---	---	---	---

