We will compare the treatment and control groups for baseline characteristics using t-tests and Chi-square tests as appropriate. Specifically, we will compare age at injury, baseline FRAX fracture risk, sex and injury level (tetraplegia/paraplegia) distribution. The level of significance for all analyses will be 0.05.

2. Evaluation of Hypotheses

Specific Aim 1: To determine the short and long term effects of zoledronic acid on BMD values of the hip, distal femur, and proximal tibia in patients with acute SCI relative to patients receiving placebo.

The primary hypothesis is that subjects treated with zoledronic acid will have at least a 50% smaller percentage decline in BMD values for the hip, distal femur and proximal tibia at 4 and 12 months post-injury than control subjects.

Analysis: For each of the bone sites to be evaluated, a percent change from baseline ([baseline BMD – follow-up BMD]/baseline BMD) will be modeled using mixed effects linear regression. Fixed effects will be included for treatment assignment, time, treatment by time interaction, and baseline BMD level. A random intercept term will be included to account for correlation among repeated measurements from the same subject. Within this regression model, we will estimate the difference between treatment groups at 4 and 12 months and test for significance of this difference. If the outcome of percent change is not normally distributed, we will apply an appropriate transformation (e.g., log, logit). If the necessary transformation is too complex for interpretation, we will consider using rank-based methods.

Secondary hypothesis 1 is that subjects treated with zoledronic acid will maintain original BMD values for the hip, distal femur and proximal tibia at 4 months and lose no more than 5% at 12 months post-injury.

Analysis: We will estimate the mean percent change at 4 and 12 months for the active treatment group along with associated 95% confidence intervals from the results of the mixed effects regression. BMD values at 4 months will be considered equivalent to those at baseline if the bounds of the confidence interval are within +/-2%. At 12 months, we will test the one-sided null hypothesis that the percentage decline is greater than 5% vs. the alternative that it is less than or equal to 5%.

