Secondary hypothesis 2 is that fractures in the hip, distal femur, and proximal tibia will be at least 50% lower in the ZA group relative to controls over the course of the grant cycle. This final hypothesis is exploratory, since we do not expect to have the numbers to achieve statistical significance given the relatively low frequency of sublesional fractures in SCI.

Analysis: The relative risks of all fractures and site-specific fractures will be calculated along with exact 95% confidence intervals. Statistical significance will be evaluated using Fisher's exact test.

Specific Aim 2: To measure and compare levels of pro-osteoclastogenic factor IL-1 β , bone formation marker P1NP, and bone resorption marker serum C terminal telopeptide of type I collagen (s-CTX) in

acute traumatic motor complete SCI subjects who receive intravenous zoledronic acid in the first 21 days post injury to the same markers in a similar group of spinal cord injury subjects receiving placebo.

The primary hypothesis is that subjects treated with zoledronic acid will have lower levels of serum marker of bone resorption s-CTX at 4 and 12 months, relative to controls. In terms of absolute marker levels, we hypothesize that the ZA subjects will have s-CTX values within the reference range at 4 and 12 months, in contrast to control subjects whose resorption marker levels will be significantly above the reference range at all of the time points.

The secondary hypothesis is that levels of serum marker of bone formation PINP will not be lower than controls at 4 and 12 months.

Analysis: We will again use mixed effects linear regression to model each marker at 1, 4 and 12 months with fixed effects for time, treatment, time by treatment interaction, and baseline biomarker level and a random subject-specific intercept. At months 4 and 12, we will estimate mean group-specific biomarker levels and associated 95% confidence intervals and test for treatment group differences. Since IL-1 β will only be measured at baseline and one month, we will use analysis of covariance to compare group averages at one month adjusted for baseline measures.

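### The Aim 2 hypothesis on P1NP at 12 months has no planned data, because P1NP is last drawn at month 4; and the plan gives no rule for concluding that P1NP is not lower

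*Combined protocol and SAP*

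**What the plan says.** The hypothesis appears twice with the same time points. Section B, Specific Aim 2, has "Levels of serum marker of bone formation P1NP will not be lower than control subjects at 4 and 12 months". Section E.2, Specific Aim 2, repeats it: "levels of serum marker of bone formation PINP will not be lower than controls at 4 and 12 months" (PINP and P1NP are the same marker).

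The Aim 2 analysis paragraph in section E.2 reads "We will again use mixed effects linear regression to model each marker at 1, 4 and 12 months". For months 4 and 12 it will "estimate mean group-specific biomarker levels and associated 95% confidence intervals and test for treatment group differences". One marker is taken out of this model: IL-1 beta "will only be measured at baseline and one month, we will use analysis of covariance to compare group averages at one month". P1NP has no such exception.

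The schedule is in section D.3, item 4. P1NP is drawn at baseline (B) and at month 1 (F). Section H covers months 4 and 12 together, but limits this marker: "Serum P1NP will also be drawn at 4 months". In Table 4 the row "P1NP ^e Study Specific" is marked at baseline, 1 month and 4 months and is blank at 8 months and 1 year. The s-CTX and iPTH rows are marked at 1 year.

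**The concern.** The hypothesis and its analysis need a 12-month P1NP value that no visit collects. If this goes unnoticed, the 12-month result will either be absent without explanation or be produced by a model with no data at that time. A sample not taken at a subject's 12-month visit cannot be recovered later.

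The second issue is the form of the claim. Saying that P1NP is *not lower* is a non-inferiority statement, yet the planned test looks for a difference and the planned intervals are for each group's mean. The plan does not say that a non-significant test will count as confirmation. It also gives no other route to the conclusion, so a modest fall in bone formation on ZA could remain unresolved.

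**Working it through.** **1. Planned P1NP data against what the hypothesis and model need**

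| Time | Required by E.2, Aim 2 | Visit text (D.3, item 4) | Table 4 |
|---|---|---|---|
| Baseline | covariate | drawn (B) | marked |
| Month 1 | modelled | drawn (F) | marked |
| Month 4 | modelled and tested | drawn (H) | marked |
| Month 12 | modelled and tested | not drawn (H restricts P1NP to month 4) | blank |

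The visit text and Table 4 agree with each other, so a broken table does not explain the gap. Planned 12-month observations: 0. If time is categorical in the mixed model, the 12-month treatment contrast cannot be estimated. If time is linear, the contrast is an extrapolation from months 1 and 4. The plan does not say which coding applies.

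**2. The plan's own sample sizes, to fix the method**

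Section D.3, item 1 sizes the trial on BMD: two-sample t-test, 2:1 allocation, 80% power, two-sided 5%. Noncentral-t power gives smallest totals of 24, 33 and 39 for effect sizes 1.3, 1.1 and 1.0, with power 81.8%, 82.3% and 81.8%. These match the stated figures. No sample size, SD or margin is given for P1NP.

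**3. What a month-4 comparison could show, in SD units**

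Inputs: N = 33 or 39 (the plan's final samples after 30% or 18% dropout) or 48 (no loss by month 4), split 22:11, 26:13 and 32:16. The documents give no month-4 attrition, so these span a range.

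- 95% CI half-width = t(0.975, N−2) × √(1/n₁ + 1/n₂). For N = 39: 2.026 × √(1/26 + 1/13) = 2.026 × 0.340 = 0.69 SD.
- Smallest margin supportable with 80% power if the groups are truly equal: noncentral t, one-sided 0.025.
- The planned model adjusts for baseline. With baseline correlation r, the residual SD is SD × √(1−r²), with N−3 degrees of freedom. The documents give no r; 0.5 and 0.7 are assumed.

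| N | CI half-width, unadjusted | Margin, unadjusted | Margin, r = 0.5 | Margin, r = 0.7 |
|---|---|---|---|---|
| 33 | 0.75 | 1.07 | 0.93 | 0.76 |
| 39 | 0.69 | 0.98 | 0.85 | 0.70 |
| 48 | 0.62 | 0.88 | 0.76 | 0.63 |

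**4. Illustration on a ratio scale**

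The documents give no P1NP SD. Assume a log-scale SD of 0.5 (range 0.4 to 0.6). At N = 39, unadjusted, the supportable margin is a ZA/placebo ratio of exp(−0.977 × 0.5) = 0.61 (0.68 to 0.56 over the SD range).

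Chance that the two-sided 5% test misses a true 30% reduction (ratio 0.7):

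| N | SD | Unadjusted | r = 0.5 | r = 0.7 |
|---|---|---|---|---|
| 33 | 0.5 | 54% | 42% | 26% |
| 39 | 0.5 | 47% (28% at SD 0.4, 60% at SD 0.6) | 34% | 18% |
| 48 | 0.5 | 37% | 25% | 11% |

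A true 50% reduction would be missed 2.2% of the time at N = 39, SD 0.5, unadjusted (8.8% at SD 0.6).

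**The case against.** Nothing in the documents answers the missing 12-month draw. Reading the analysis sentence as covering each marker only where it is measured does not help, because the hypothesis itself names 12 months.

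The second point is more open to challenge. The wording can be taken as a directional prediction about a secondary biomarker rather than a formal non-inferiority claim, and section A presents the biomarker outcome as observational. The plan never equates non-significance with proof. Its one interval rule, "BMD values at 4 months will be considered equivalent to those at baseline if the bounds of the confidence interval are within +/-2" percent, concerns stability within the ZA group, so it is an imperfect precedent for a between-group comparison. The mixed model already yields the adjusted contrast. The power illustration depends on an assumed SD and on a 30% effect that the plan does not name. The only P1NP effect in the documents is a 58% fall from baseline at 12 months in post-menopausal women given ZA (section C, previous trials). A between-group difference that large would be missed about 0.1% of the time at N = 39, SD 0.5, unadjusted (1.4% at SD 0.6).

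Most of this stands. It makes the *not lower* point minor and argues against setting up a formal non-inferiority test. It does not supply a way to conclude *not lower* from a difference test. The 58% figure is a before/after change in another population, so it does not settle what to expect against placebo here.

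**Conclusion.** The concern holds. The 12-month half of the P1NP hypothesis has no planned data: 0 observations, at 1 of 2 hypothesised time points. This needs no assumption; it follows from comparing the hypothesis and analysis with the visit text and Table 4.

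The missing decision rule is secondary. At month 4 the trial could support only a wide margin: 0.88 to 1.07 SD unadjusted, or 0.63 to 0.93 SD under the assumed baseline correlations. It would detect a large fall in P1NP but could leave a modest one open. The ratio-scale figures rest on the assumed log SD and are illustrative.

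The scope is one secondary hypothesis. The BMD primary outcome is untouched, s-CTX has its 12-month draw, and month-4 P1NP has planned data.

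**What to change.** Reconcile the passages in one of two ways.

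- **Collect it.** Add P1NP to the 12-month sample already drawn for s-CTX and iPTH, amend section H, and mark 1 year in the P1NP row of Table 4. Cost: one assay per subject, at most 48. Section H already runs this panel plus P1NP at month 4 under the same 25 ml limit.
- **Drop it.** Remove 12 months from the P1NP hypothesis in sections B and E.2, and state that P1NP is modelled at months 1 and 4 only, in the way IL-1 beta is already handled. Cost: none beyond the edit.

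Under either option, add a sentence or two to the Aim 2 analysis: report the baseline-adjusted ZA-versus-placebo difference or ratio in P1NP with its 95% confidence interval, label it as estimation, and state that a non-significant test will not be read as showing that P1NP is not lower. A formal margin is not recommended, because this sample could support only a very wide one.

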In the patient with SCI, the primary goal of osteoporosis is fracture prevention. Although the annual incidence of lower extremity bone fractures has been reported as 2-6%^{3,11,14} the above figures may be underestimated^{5,14,15} since many subjects present to local hospitals rather than major spinal cord injury centers for evaluation and treatment³. Among those with chronic SCI, 25-49% ultimately experience a fragility fracture^{14,16}. The majority of fragility fractures occur in the hip, distal femur and proximal tibia^{5,7,14}. Fractures may arise from routine activities such as transfers or low-velocity falls from a wheelchair or commode^{3,7,17}. Maintenance of bone mass is essential to fracture prevention given the morbidity that can result: hospitalization, increased spasticity, autonomic dysreflexia, heterotopic ossification, and in select cases, surgical intervention⁸. In those fractures treated conservatively, pressure ulcers may arise from bracing or splints, temporary casts, or bed rest⁷. The consequences invariably lead to reduced level of independence, increased nursing or attendant care, and greater cost to the patient and health care system. With the combined effects of an increased life expectancy after SCI and a greater number of new cases among persons above age 55, who may have already developed early osteoporosis, the cost physically and emotionally to the patient and financially to the health care system will rise in coming years^{7,18}.

Pathophysiology of Osteoporosis:

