Information on Physical Examinations and Clinical Assessments

Objective Evaluations: To ensure the patient has a complete spinal cord injury (AIS Grade A), investigators will perform a complete neurological exam according to ISNCSCI guidelines as part of initial screening (days 2-17 post injury). A confirmatory exam will be conducted in the 24 hours prior to study drug delivery. At the end of the study when the patient returns for final laboratory tests and DXA scan, a repeat neurological examination will be performed.

Subjective reports: Interviews will be conducted with patients every 2 months during the first year, either in person if testing is scheduled, or by phone between testing sessions. The first phone call will occur 2 months from injury if the subject is not an inpatient or not available for in-person interview. During these interviews, subjects will be asked about any evidence or knowledge of bone fractures since the previous contact. We will obtain information about exercises and standing, (including use of FES), such as how often and average daily duration.

Follow up for Subsequent Years of Grant Cycle

During the subsequent years of the grant cycle, patients will be contacted every 6 months for information on fractures sustained in the prior 6 months. As part of the consent form, we will be requesting permission to receive x-ray reports of any bone fracture experienced and mechanism of injury between years 1 and 4 post injury and collect information on participation in standing, lower extremity exercise and functional electrical stimulation (FES), and current calcium and vitamin D use.

[figure not shown]
Early Termination

Should a subject gain neurological function prior to initial drug administration and no longer have a complete SCI, that potential subject is withdrawn from the study. Should a subject recover neurological function and the SCI be deemed incomplete any time after the study drug has been administered, that participant will continue with all assessments and follow up studies without exception.

5. DXA Scan Analyses

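### After year 1 the fracture question covers a fixed six months, so a missed contact can leave an interval that is never asked about

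*Combined protocol and SAP*

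**What the plan says.** The protocol states the recall period for fractures in two ways.

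- **Year 1.** Interviews take place every two months, and under Subjective reports "subjects will be asked about any evidence or knowledge of bone fractures since the previous contact". The questionnaire for months 2, 6 and 10 (D.3, item 4, part G) uses the same open window: "Any evidence or knowledge of bone fractures since the previous contact".
- **After year 1.** Under Follow up for Subsequent Years of Grant Cycle, "patients will be contacted every 6 months for information on fractures sustained in the prior 6 months".

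Table 5 schedules six contacts in years 2-4, at months 6 and 12 of each year. It lists fracture questions at each one but gives no recall window. The day tolerances in Table 4 end at one year. No tolerance, make-up contact or missed-contact rule is stated for the later years.

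The analysis is in section E.2, Specific Aim 1, secondary hypothesis 2: "The relative risks of all fractures and site-specific fractures will be calculated along with exact 95% confidence intervals", with Fisher's exact test, over the whole grant cycle. It does not use person-time and does not say how intervals without information are handled. The hypothesis is labelled exploratory.

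**The concern.** An open window repairs itself: a subject who misses one call and answers the next is asked about the whole time between. A fixed window as long as the spacing has no overlap, so it cannot do this. Take a subject who misses the month-18 contact and answers at month 24. Read literally, the month-24 question covers months 18-24, and months 12-18 are never asked about although the subject is back in touch. A late contact leaves a gap as long as the delay. If the month-12 contact is missed, the month-18 question reaches back only to month 12, although the last completed contact may have been at month 10.

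The subject's own answer is likely to be the main source of fracture data. The Background says that published incidence may be too low "since many subjects present to local hospitals rather than major spinal cord injury centers for evaluation and treatment", and no search of outside records independent of the subject's report is described. With so few fractures expected, losing even one visibly moves a relative risk.

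**Working it through.** The plan gives no figure for missed contacts or fracture ascertainment, so there is none to reproduce. Its sample-size figures concern bone mineral density and are not affected.

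**Inputs from the documents**
- 48 subjects randomized 2:1, so 32 on ZA and 16 on placebo (section D; D.3, item 1).
- Annual incidence of lower-extremity fracture 2-6% (section C).
- Hypothesised halving on ZA (section B, secondary hypothesis 2).
- Six contacts over the three years 2-4 (Table 5).

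**Assumptions**
- Each contact is missed independently with probability *m*. The documents give no value, so 5-30% is shown.
- All 48 subjects complete years 2-4. This is an upper bound, because enrollment runs over 4 years of a 5-year timetable.

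**Step 1: expected fractures in years 2-4**
- Placebo: 16 × 3 × 0.02 = 0.96 to 16 × 3 × 0.06 = 2.88.
- ZA: 32 × 3 × 0.01 = 0.96 to 32 × 3 × 0.03 = 2.88.
- Total: 1.92 to 5.76.

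**Step 2: share of years 2-4 left uncovered**
- Fixed window: an interval is uncovered when its own contact is missed, so the share is *m*.
- Open recall: an interval is uncovered only when its own contact and every later one are missed, so the share is (m + m² + … + m⁶)/6.
- At m = 0.20: (0.20 + 0.04 + 0.008 + 0.0016 + 0.00032 + 0.000064)/6 = 0.249984/6 = 4.2%, against 20%.

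**Step 3: expected fractures in uncovered intervals** (share × total from step 1)

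| m | Uncovered, fixed | Uncovered, open | Fractures, fixed | Fractures, open |
|---|---|---|---|---|
| 5% | 5% | 0.9% | 0.10-0.29 | 0.02-0.05 |
| 10% | 10% | 1.9% | 0.19-0.58 | 0.04-0.11 |
| 20% | 20% | 4.2% | 0.38-1.15 | 0.08-0.24 |
| 30% | 30% | 7.1% | 0.58-1.73 | 0.14-0.41 |

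The chance that a subject misses at least one of the six contacts is 1 − (1 − m)⁶, which is 47% at m = 0.10 and 74% at m = 0.20.

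**Step 4: limits of the gain**
- Open recall recovers only misses that are followed by a completed contact. If every miss were part of permanent loss to follow-up, it would recover nothing.
- Subjects enrolled late have fewer contacts and gain less. With two contacts and m = 0.20 the open-recall share is (0.20 + 0.04)/2 = 12%, against 20%.

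**Step 5: what the fracture comparison can show in any case**
- Three-year risks at 2% per year: 1 − 0.98³ = 5.9% on placebo and 1 − 0.99³ = 3.0% on ZA.
- At 6% per year: 1 − 0.94³ = 16.9% and 1 − 0.97³ = 8.7%.
- With 16 and 32 subjects and complete data, Fisher's exact test at two-sided 0.05 has power of about 3% and 12%.

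**The case against.** The strongest reply is that the later-years sentence is narrative, not the questionnaire. For contacts six months apart it may simply describe the interval between them, and nothing bars staff from recording an older fracture that a subject mentions. The data collection forms, which the protocol places in an Appendix B, are not in the available text. This has force. A reader might infer that fractures in a gap are certain to be lost, but the documents show only that the stated rule does not ask about them. The rule is still explicit, it differs from the year-1 wording, and no make-up rule sits beside it.

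Other routes could pick up a fracture. Adverse events are followed until resolution, and serious ones, including those requiring hospitalization, must be reported, with no six-month limit. Permission is also sought for x-ray reports. Both depend on the team hearing of the fracture, and the active side-effect interviews stop one month after infusion. These routes reduce the gap without closing it.

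Four stronger readings are tempting, and the documents do not support them:

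- **First-year fractures go unverified.** The permission covers "receive x-ray reports of any bone fracture experienced and mechanism of injury between years 1 and 4 post injury", which can include year 1, and the consent wording is not in the available text.
- **Subjects cannot feel fractures at these sites.** Table 3 defines grade A by absent function at S4-S5. An unnoticed fracture would in any case be missed under either wording.
- **All expected fractures are at risk.** Expected fractures are not lost fractures; only those in uncovered intervals count.
- **The relative risk is biased.** A gap common to both arms mainly costs events and precision. Bias needs missed contacts that differ by arm or are related to fracture, and nothing in the documents shows either. It is also only an inference that an unasked interval would be counted as fracture-free, because no denominator rule is stated.

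**Conclusion.** The point holds as a minor, inexpensive improvement. Read literally, the fixed window lets a missed or late contact in years 2-4 leave time uncovered even when the subject is reached again, and the analysis makes no allowance for this. With 20% of contacts missed, the uncovered share of years 2-4 would be 20% as written and about 4% with open recall; at 10% missed, 10% and about 2%. In fractures, the 20% case means about 0.4-1.2 of 1.9-5.8 expected, against about 0.1-0.2. These figures rest on an assumed, independent miss rate, the 2-6% background incidence, a halving on ZA, and complete follow-up of all 48 subjects, which makes the counts upper bounds.

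If every contact is on schedule the two wordings are equivalent and nothing is lost. The outcome is exploratory and the plan itself does not expect significance. The bone density endpoints, sample size and type I error are untouched.

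**What to change.** At every contact in years 2-4, ask about fractures since the date of the last completed contact, and record that date. This carries the year-1 approach forward and also covers a missed month-12 contact. The recorded dates show which intervals remain unobserved, so section E.2 can add a sentence on how those are handled in the relative risks.

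The cost is one changed phrase, one date field and one analysis sentence, with no extra contacts. The downside is a longer recall period after a missed call, with somewhat less reliable dating. The change is best made before the later contacts take place, since intervals never asked about are hard to reconstruct.
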